1.5.3 Other Safety Considerations for the Combination

Pre-renal and Intrinsic Renal Failure

In Part C of study 113220, 1 subject (150mg/1mg) experienced grade 2 renal failure and 4 (at the 150mg/2mg doses) experienced grade 3 renal failure. In study MEK115306, the incidence of renal failure events was similar (3% in the combination and 2% for dabrafenib monotherapy).

Pancreatitis

Six subjects in BRF113220 had acute pancreatitis or pancreatitis, 3 of which were grade 4 and considered related to study treatment. [6] The time to onset to pancreatitis occurred at a median of 138 days. One event of pancreatitis was reported in each treatment arm of study MEK115306.

Hemorrhage

Combination treatment resulted in an increased incidence and severity of hemorrhagic events: 16% (9/55) of patients treated with the combination compared with 2% (1/53) of patients treated with dabrafenib alone. Intracranial hemorrhage was fatal in two (4%) patients receiving the combination.

Venous Thromboembolic Events

Treatment with the combination of trametinib and dabrafenib resulted in an increased incidence of deep vein thrombosis (DVT) and pulmonary embolism

(PE): 7% (4/55) of patients compared with none of the 53 patients treated with dabrafenib as a single agent. One (2%) patient receiving combination therapy experienced a fatal pulmonary embolism.

Hyperglycemia

Hyperglycemia may increase in occurrence when combination trametinib and dabrafenib are used. The incidence of Grade 3 hyperglycemia based on laboratory values was 5% (3/55) in patients treated with dabrafenib in combination with trametinib compared with 2% (1/53) in patients treated with dabrafenib as a single agent.

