3.2.9 Pulmonary embolism on active therapy

3.2.10 History of interstitial lung disease or pneumonitis

3.2.11 Known HIV, Hepatitis B or C infection (with the exception of chronic or cleared HBV and HCV infection, which will be allowed provided the following tests are done at screening: viral hepatitis serology, Hepatitis B surface antigen and Hepatitis B core antibody (IgM) and/or Hepatitis C RNA)

3.2.12 Currently active GI disease, or prior surgery that may affect ability to absorb oral medications

3.2.13 History or current evidence/risk of retinal vein occlusion (RVO) or retinal pigment epithelial detachment (RPED):

- Predisposing factors to RVO or RPED (e.g. uncontrolled glaucoma or ocular hypertension, uncontrolled systemic disease such as hypertension, diabetes mellitus, or history of hyperviscosity or hypercoagulability syndromes)
- Visible retinal pathology as assessed by ophthalmic exam that is considered a risk factor for RVO or RPED such as:
 - Evidence of new optic disc cupping
 - Evidence of new visual field defects
 - Intraocular pressure > 21 mm Hg

3.2.14 Currently receiving cancer therapy (chemotherapy, radiotherapy, immunotherapy, or biologic therapy) **NOTE:** palliative radiation therapy is permitted for non-target lesions that are either new or present at baseline provided total dose does not exceed 30 Gy; however, radiation skin injury has been reported with concurrent use of dabrafenib and radiation. See concomitant medications section 4.5.3 for recommendations when palliative radiation is prescribed.

3.2.15 Use of other prohibited medications within 5 half-lives or 14 days prior to the first dose of study drugs or requires any of these medications while receiving medication on this study (see section 4.5)

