4.4.8 Management and Dose Modification Guidelines for Therapy-related Pyrexia

Pyrexia is defined as $\geq 38.5^{\circ}\text{C}$ or 101.3°F . Episodes of pyrexia have been observed in subjects receiving dabrafenib monotherapy and is increased in incidence and severity in subjects receiving dabrafenib in combination with trametinib. (Pyrexia is also a side effect of trametinib, but is less frequent than that associated with dabrafenib-see section 5.1.5). [6] In a minority of cases the pyrexia was accompanied by symptoms such as severe chills, dehydration, hypotension, dizziness or weakness. Pyrexia accompanied by hypotension, dehydration requiring IV fluids, or severe rigors/chills should be reported as an SAE (see section 7.3.3). Subjects should be instructed on the importance of immediately reporting febrile episodes. In the event of a fever, the subject should be instructed to take non-steroidal anti-pyretics (e.g., ibuprofen), acetaminophen or other suitable anti-pyretic medication as appropriate to control fever. The use of oral corticosteroids should be considered in those instances in which anti-pyretics are insufficient. In subjects experiencing pyrexia associated with rigors, severe chills, dehydration, hypotension, etc., renal function should be monitored carefully.

For each episode of pyrexia (defined above), a thorough clinical examination (including blood pressure) for signs and symptoms of infection or hypersensitivity is required; laboratory work-up should include full blood count, electrolytes, creatinine, BUN, CRP, liver function tests, blood culture, and urine culture. For subjects experiencing pyrexia complicated by rigors, severe chills, etc., a clinical evaluation and laboratory work-up is mandatory for each event; anti-pyretic treatment should be started immediately at the first occurrence and prophylactic anti-pyretic treatment is recommended. This prophylactic treatment may be discontinued after 3 days in the absence of pyrexia.

Oral hydration should be encouraged in subjects without evidence of dehydration. Intravenous hydration is recommended in subjects experiencing pyrexia complicated by dehydration/hypotension.

Pyrexia Management	Action and Dose Modification

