4.4.11 Hyperglycemia

Hyperglycemia requiring an increase in the dose of, or initiation of insulin or oral therapy can occur with dabrafenib. Monitor serum glucose levels as clinically appropriate during treatment with dabrafenib in subjects with pre-existing diabetes or hyperglycemia. Advise patients to report symptoms of severe hyperglycemia such as excessive thirst or any increase in the volume or frequency of urination.

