^{3a} Repeat ophthalmic exams annually while on treatment and if clinically-indicated due to the presence of ocular symptoms. The exams will be performed one year after the day 1 cycle 8 visit +/- 2 months and every year thereafter until the patient is off treatment. See Appendix G (section 11.7) for Ophthalmic Exam Worksheet.

⁴The end of treatment visit should only occur when patients permanently stop study treatment and should be performed 30 days (+/-7 days) after the last dose of study medication. All adverse events and concomitant medications should be followed up until the 30-day End of Treatment (EOT) visit. Patients who have an ongoing \geq grade 2 or serious AE (SAE) at the EOT will continue to be followed until the event is resolved or deemed irreversible by the investigator. See section 6.5 for follow-up schedule for patients who discontinue study treatment due to progression or for other reasons.

⁵Complete history at baseline only, thereafter focused history on symptoms/toxicity; physical exam to include height (baseline only), weight, and vital signs

⁶Dermatologic exams will continue every 3 months for the first 6 months following discontinuation from dabrafenib, and should include monitoring for cutaneous and non-cutaneous secondary/recurrent malignancies.

⁷Serum B-HCG within 48 hours prior to first dose of study medication for WOCBP; serum B-HCG will be repeated only if clinically appropriate.

⁸**Hematology:** CBC with differential, Hgb, and platelet count; **Serum chemistries:** creatinine, sodium, potassium, calcium, magnesium, phosphorus, LDH and albumin. **Liver function tests:** total bilirubin, AST (SGOT) and ALT (SGPT). Also see sections 4.4.9.3 and 11.4.4 for required monitoring in event of liver toxicities, including possibility of blood draw for pharmacokinetics. If screening evaluations of these tests are performed within 48 hours prior to Day 1 of treatment, they do not need to be repeated.

⁹Coagulation profile includes prothrombin time or INR, and activated partial thromboplastin time.

¹⁰Toxicity assessment should include interrogation of the patient related to any visual changes they may be experiencing. Patients who have an ongoing \geq grade 2 or serious AE (SAE) at the time of discontinuation from treatment will continue to be followed until the event is resolved or deemed irreversible by the investigator.

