6.2 Pre-Study Assessments

Please see section 6.7 regarding collection of a single blood sample at some point over course of study for germline DNA.

Clinical evaluation: complete history, physical examination (to also include vital signs, height, and weight), dermatologic exam (including full body skin exam), ophthalmic exam (See Appendix G (section 11.7) for Ophthalmic Exam Worksheet), and ECOG performance status.

Laboratory studies:

- **Pregnancy Test:** A serum pregnancy test (β -HCG) is required for all women of childbearing potential at screening within 48 hours prior to the first dose of study treatment. Note: Postmenopausal women must have had amenorrhea for ≥ 12 months in order to be considered “of non-childbearing potential.” This should be documented appropriately in the patient’s medical history.
- **Hematology:** Hematology includes the following parameters: complete blood count (CBC) with differential, hemoglobin (Hgb), and platelet count.
- **Coagulation Profile:** The coagulation profile includes prothrombin time or INR, and activated partial thromboplastin time.
- **Serum Chemistries and LFTs:** These include the following parameters: creatinine, sodium, potassium, calcium, magnesium, phosphorus, LDH, albumin, total bilirubin, AST (SGOT) and ALT (SGPT)

Cardiac monitoring: 12-lead ECG, ECHO (preferred) or MUGA

Concomitant medications: Documentation of all concomitant medications, and in particular any prohibited drugs and drugs to be used with caution as listed in the appendices (see section 11.2). **NOTE:** Patients will be given a list of medications that are prohibited and/or should be used with caution as a separate document. Patients will be informed that these drugs may interact with trametinib or dabrafenib, and may increase or decrease their toxicity.

Patient Diary: Patients will be provided diary (as separate document) and instructed to record the time and date of each dose of study medication. Diary will be reviewed during study visits. See Appendices, section 11.6, for a model diary.

Toxicity assessment: Using NCI CTCAEv4 for baseline documentation

Tissue acquisition: Sufficient frozen tissue remaining from diagnostic biopsy or willing to undergo biopsy for research purposes. See section 6.7 and laboratory manual.

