6.5 End of Treatment

This visit should occur in patients when they permanently stop treatment for any reason, and should be performed 30 days (+/-7 days) after the last dose of study medication.

Clinical evaluation: complete history, physical examination (to also include vital signs and weight), and ECOG performance status.

Laboratory studies:

- **Hematology**: Hematology includes the following parameters: CBC with differential, Hgb, and platelet count.
- **Serum Chemistries**: These include the following parameters: creatinine, sodium, potassium, calcium, magnesium, phosphorus, albumin, total bilirubin, AST (SGOT) and ALT (SGPT).

Concomitant medications: Review any additions or deletions

Patient Diary: Review Diary

Toxicity Assessment: Using NCI CTCAEv4; Patients who have an ongoing grade 4 or serious AE (SAE) at the time of discontinuation from treatment will continue to be followed until the event is resolved or deemed irreversible by the investigator, and will then be followed-up per protocol. Toxicity assessment should include interrogation of the patient related to any visual changes they may be experiencing.

Tissue acquisition: Biopsy of accessible tumor will be done in patients who stop treatment due to progression, if possible within 7 business days of documented disease progression, and optimally within 4 hours of taking that day's study medication. Post-treatment biopsies will not be required for patients removed for reasons other than disease progression. See section 6.7 and laboratory manual.

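### No scheduled chemistry list names glucose, so the trial's count of hyperglycemia, a risk its own background describes, would be a lower bound

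*Combined protocol and SAP*

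**What the plan says.** **Scheduled tests.** Footnote 8 of the Time and Events Table (section 6.1) gives the serum chemistries as "creatinine, sodium, potassium, calcium, magnesium, phosphorus, LDH and albumin", and adds total bilirubin, AST and ALT as liver function tests. Sections 6.2 (screening) and 6.3.1 (on treatment) list the same 11 analytes. Section 6.5 (end of treatment) lists 10 of them, without LDH. Glucose is in none of the four lists.

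**The risk.** Section 1.5.3 says: "Hyperglycemia may increase in occurrence when combination trametinib and dabrafenib are used". It continues: "The incidence of Grade 3 hyperglycemia based on laboratory values was 5% (3/55) in patients treated with dabrafenib in combination with trametinib", against 2% (1/53) on dabrafenib alone. Section 5.2.7 reports laboratory-based grade 3 hyperglycemia of 6% on dabrafenib against 0% on dacarbazine. Appendix H lists hyperglycemia among the adverse events of special interest in MEK115306.

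**What is asked of sites.** Section 4.4.11 says: "Monitor serum glucose levels as clinically appropriate during treatment with dabrafenib in subjects with pre-existing diabetes or hyperglycemia". Section 5.2.7 repeats this. Both also ask that patients be told to report symptoms of severe hyperglycemia. Neither sets a schedule, and 4.4.11 has no action table.

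**The concern.** The monitoring instruction in 4.4.11 and 5.2.7 is confined to a group defined by history: patients already known to have diabetes or hyperglycemia. No protocol-required screening test shows who else belongs to that group. For everyone outside it, the only detection route the protocol specifies is the patient noticing and reporting symptoms of severe disease.

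What is at stake is how the safety data can be read. Section 6.8 makes every treated patient evaluable for toxicity under CTCAE, and section 7.4 sends safety data to the data and safety monitoring committee. A low or zero hyperglycemia count could mean that the event was rare, or that glucose was seldom measured. A reader who set that count beside the laboratory-based rates in 1.5.3 and 5.2.7 would be comparing two different methods of ascertainment.

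**Working it through.** **Step 1. Is glucose requested anywhere on a schedule or as part of a defined work-up?**

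| Place | Purpose | Glucose named? |
|---|---|---|
| 3.1.6 | Organ-function eligibility | No |
| 6.1, footnote 8 | All scheduled chemistries | No |
| 6.2 | Screening panel | No |
| 6.3.1 | On-treatment panel | No |
| 6.5 | End-of-treatment panel | No |
| 4.4.8 | Fever work-up | No |
| 11.4.1 | Liver-event work-up | No |
| 4.4.11 and 5.2.7 | Known diabetes or hyperglycemia | Yes, unscheduled |

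The fever entry reads: "laboratory work-up should include full blood count, electrolytes, creatinine, BUN, CRP, liver function tests, blood culture, and urine culture". The omission is the same in all four scheduled lists, so it is not a slip in one footnote.

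**Step 2. Reproduce the quoted rates.**

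- Section 1.5.3, grade 3 by laboratory value: combination 3/55 = 5.45% (stated 5%); dabrafenib 1/53 = 1.89% (stated 2%).
- Appendix H, any grade: combination 13/209 = 6.2% (stated 6); dabrafenib 2/211 = 0.95% (stated <1).
- Appendix H, grade 3: combination 4/209 = 1.9% (stated 2); dabrafenib 1/211 = 0.47% (stated <1).

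All agree with the stated rounding.

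**Step 3. What might occur in 20 patients?** The sample size of 20 is from sections 1.1 and 1.7. With a per-patient rate p and independent patients, the expected number of cases is 20p, and the chance of at least one is 1 − (1 − p)^20.

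| Rate used | p | Expected cases | Chance of at least one |
|---|---|---|---|
| Grade 3, Appendix H, 4/209 | 0.0191 | 0.38 | 1 − 0.9809^20 = 32% |
| Grade 3, section 1.5.3, 3/55 | 0.0545 | 1.09 | 1 − 0.9455^20 = 67% |
| Any grade, Appendix H, 13/209 | 0.0622 | 1.24 | 1 − 0.9378^20 = 72% |

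These are chances that a case occurs. The chance that one is missed depends on how often sites test locally and how often cases cause symptoms, and the documents give neither.

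**The case against.** The best defence is that the protocol does address glucose. Sections 4.4.11 and 5.2.7 set the same targeted policy, and a fixed panel without glucose is compatible with it. This stands in part: the sections do not contradict one another outright. The policy still depends on knowing who has hyperglycemia at entry, and no required test establishes that.

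Several stronger readings are tempting and go beyond the documents:

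- *That protocol rules cannot operate without a glucose value.* No rule states a glucose threshold. Section 3.2.13 names "uncontrolled systemic disease such as hypertension, diabetes mellitus" as an example of a predisposing factor for retinal vein occlusion or retinal pigment epithelial detachment, and this can be judged from the complete history required by 6.2. The grade-based table in 4.4.12 may cover hyperglycemia, but the protocol does not say so.
- *That hyperglycemia cannot be graded.* Any glucose obtained under 4.4.11 or in local care can be graded. The CTCAE criteria for this event are not in the documents.
- *That the lists forbid glucose.* The wording of 6.2, 6.3.1 and 6.5 can be read as a minimum set. Footnote 8 simply lists the analytes.
- *That the chance of a case is 64–71%.* This comes from the rounded 5% and 6% (1 − 0.95^20 and 1 − 0.94^20). It mixes grade 3 with any grade and omits the lower grade 3 rate of 4/209.
- *That the combination is shown to raise the risk over dabrafenib.* Section 1.5.3 says only that it may, and 3/55 against 1/53 is a difference of two patients. Section 5.2.7 gives 6% grade 3 on dabrafenib alone. The any-grade figures in Appendix H do point towards an increase.

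It is also fair to say that no stated objective is a safety rate and that section 8.1 plans no hyperglycemia estimate.

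**Conclusion.** The point holds as a modest gap in safety ascertainment. Under protocol-required testing, undiagnosed baseline hyperglycemia goes unidentified, and new-onset hyperglycemia in patients without a known history is found only through reported symptoms. The trial's count would be a lower bound and not comparable with the laboratory-based rates in 1.5.3 and 5.2.7.

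The shortfall cannot be sized from the documents. The 32% to 72% range shows only that a case among 20 patients is plausible. It assumes that the quoted rates carry over to this population, that patients are independent, and that exposure and ascertainment resemble the source studies. Appendix H does not say whether its counts are laboratory-based.

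A reader might infer that patients are left without any glucose monitoring or that the trial's conclusions are at risk. Neither follows: 4.4.11 covers known cases, local tests may find others, and the kinome, mutation, response and survival objectives do not use glucose.

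**What to change.** Reconcile 4.4.11 and 5.2.7 with the laboratory lists in 6.1 (footnote 8), 6.2, 6.3.1 and 6.5. The sponsor can do this in either of two ways:

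1. List glucose among the analytes measured on the chemistry samples already drawn. This needs no extra visit or draw; the cost is one more analyte to record and review.
2. Leave the lists as they are and state in the safety reporting that laboratory hyperglycemia is not systematically ascertained, so its count is a lower bound and should not be set against the laboratory-based rates in the background. This costs a sentence, but the gap stays.

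Neither option changes a statistical figure in the plan. No dose, glucose threshold or management rule is proposed.

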6.2 Pre-Study Assessments

Please see section 6.7 regarding collection of a single blood sample at some point over course of study for germline DNA.

Clinical evaluation: complete history, physical examination (to also include vital signs, height, and weight), dermatologic exam (including full body skin exam), ophthalmic exam (See Appendix G (section 11.7) for Ophthalmic Exam Worksheet), and ECOG performance status.

Laboratory studies:

- **Pregnancy Test:** A serum pregnancy test (β -HCG) is required for all women of childbearing potential at screening within 48 hours prior to the first dose of study treatment. Note: Postmenopausal women must have had amenorrhea for ≥ 12 months in order to be considered “of non-childbearing potential.” This should be documented appropriately in the patient’s medical history.
- **Hematology:** Hematology includes the following parameters: complete blood count (CBC) with differential, hemoglobin (Hgb), and platelet count.
- **Coagulation Profile:** The coagulation profile includes prothrombin time or INR, and activated partial thromboplastin time.
- **Serum Chemistries and LFTs:** These include the following parameters: creatinine, sodium, potassium, calcium, magnesium, phosphorus, LDH, albumin, total bilirubin, AST (SGOT) and ALT (SGPT)

Cardiac monitoring: 12-lead ECG, ECHO (preferred) or MUGA

Concomitant medications: Documentation of all concomitant medications, and in particular any prohibited drugs and drugs to be used with caution as listed in the appendices (see section 11.2). **NOTE:** Patients will be given a list of medications that are prohibited and/or should be used with caution as a separate document. Patients will be informed that these drugs may interact with trametinib or dabrafenib, and may increase or decrease their toxicity.

Patient Diary: Patients will be provided diary (as separate document) and instructed to record the time and date of each dose of study medication. Diary will be reviewed during study visits. See Appendices, section 11.6, for a model diary.

Toxicity assessment: Using NCI CTCAEv4 for baseline documentation

Tissue acquisition: Sufficient frozen tissue remaining from diagnostic biopsy or willing to undergo biopsy for research purposes. See section 6.7 and laboratory manual.

Tumor measurement: Tumor measurement or imaging should remain consistent throughout study, and will include contrasted computed tomography (CT) scan of chest, abdomen and pelvis. These tests may be performed ± 7 days of the scheduled day. At screening, an MRI of the brain is required.

Brain scan: At screening, a scan of the brain is required; MRI unless contraindicated, in which case a CT scan with contrast may be substituted.

6.3 Treatment Assessments

6.3.1 Day 1 of each 3-week cycle until cycle 9, and then D1 of every odd numbered cycle thereafter

Clinical evaluation: focused history, physical examination (to also include vital signs, and weight), and ECOG performance status.

Laboratory studies:

- **Hematology**: Hematology includes the following parameters: complete blood count (CBC) with differential, hemoglobin (Hgb), and platelet count.
- **Serum Chemistries and LFTs**: These include the following parameters: creatinine, sodium, potassium, calcium, magnesium, phosphorus, LDH, albumin, total bilirubin, AST (SGOT) and ALT (SGPT).

Concomitant medications: Review any additions or deletions

Patient Diary: Review Diary

Toxicity Assessment: Using NCI CTCAEv4; toxicity assessment should include interrogation of the patient related to any visual changes they may be experiencing.

6.3.2 Day 1 of every other 3-week cycle starting with Cycle 3 until end of treatment

Clinical evaluation: Dermatologic exam

Tumor measurement: Tumor measurement or imaging should remain consistent throughout study, and will include contrasted computed tomography (CT) scan of chest, abdomen and pelvis. These tests may be performed ± 7 days of the scheduled day.

Note: The frequency of tumor assessment scans reduced to every 12 weeks for subjects responding to combination therapy after cycle 9; For subjects responding to combination therapy for > 2 years, the frequency of disease assessment scans should be reduced to every 6 months.

6.3.3 Day 1 of Cycles 3, 5, 9, 13 and every 4th cycle thereafter

Cardiac monitoring: 12-lead ECG and ECHO

